Walking impairment is a signature characteristic of MS, and of progressive MS in particular. Estimates of the prevalence of gait impairment in MS range from approximately 40-80%, and MS patients rate walking difficulties as one of the most burdensome aspects of the disease (20). Multiple walking assessment methods have been developed and evaluated in MS, including the gait-specific measures included in the present study: the 6MWT (21), the T25FW (22), the MSWS-12 (23) and the AI (24).

There is no clear "best" objective assessment of ambulation in MS. The most commonly used metrics are the EDSS (an overall measure of MS-related disability that is heavily "weighted" toward walking ability) and the T25FW. The T25FW is, as the name implies, a timed measurement of how fast a patient can safely walk 25 feet. Thus, it is primarily a measure of walking *speed*. In contrast, the 6MWT (a measure of the distance a subject can walk in 6 minutes) is a test of walking *endurance*. While impairments in walking speed certainly may cause problems in daily living for MS patients (e.g. crossing the street, getting to the bathroom on time), impairments in walking endurance probably account for the majority of walking-related functional limitations in MS. Several studies have evaluated and compared these metrics, and found both to be valid and reliable (25, 26). These studies found high correlations between walking speed and walking distance, but recommended a test of walking distance such as 6MWT be included in intervention studies where ambulatory function is an important outcome (as in the present study) (25). The 6MWT is more likely to capture the effect of motor fatigue on walking ability than is the T25FW, and is likely less susceptible to floor effects from subjects with no (or mild) gait impairment (27).

The literature contains much more data on T25FW than on 6MWT in MS patients. In particular, there is no published data on the change in 6MTW in MS patients over time. Therefore, change in the T25FW will serve as the primary endpoint of the study. Multiple studies have found that a change of 20% from baseline T25FW is both reliably detectable and clinically meaningful (28-31). **The primary endpoint of this study will be the proportion of subjects in each treatment arm who show a 20% increase in T25FW at the last study visit, compared to baseline.** Changes in 6MWT, MSWS-12, and AI will be secondary endpoints.

B. Safety and Tolerability

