2. Extrapolated to a 3 year follow up period, 60% of progressive MS patients will show a 20% or greater increase in T25FW.

Utilizing a significance level of 0.05 and equal sample sizes, 42 subjects per treatment arm would provide 80% power to detect a 50% difference in the proportion of subjects reaching the threshold of 20% worsening in T25FW ($P1 = 0.6$, $P2 = 0.3$, $\alpha = 0.05$, $\beta = 0.2$, 2-sided test). Given the length of the study, we anticipate a dropout rate of up to 10-20% of randomized subjects. To account for this possibility, a total sample size of 100 subjects (50 per treatment arm) will be randomized.

C. Randomization

The study will utilize blocked randomization stratified by study center, with equal (1:1) allocation to the ACTH and control groups.

D. Blinding

Study subjects, their referring physicians, the study monitor, and all study personnel who come in contact with study subjects (including site principal investigators, examining neurologists, study coordinators, nurses, and other study staff and their designated backups) will be blinded to treatment allocation. One investigator who will not come in direct contact with study subjects ([name]) as well as the study statistician and other members of the Data Safety Monitoring Board (DSMB, see section 7F) will be unblinded, to allow for assessment of any safety concerns that may arise over the course of the study.

E. Data Analysis Plan

Descriptive analyses of baseline characteristics and all outcome measures (primary and secondary) will include means with standard deviations or medians with ranges for continuous variables depending on the parametric or non-parametric distribution of the variables, and frequencies with percentages for categorical variables. Between group (ACTH and placebo) comparisons of baseline characteristics and baseline outcome measures will be done using two sample t-tests or Wilcoxon rank sum tests for parametric and non-parametric continuous variables, respectively, and Chi-square tests or Fisher's exact tests for categorical variables.

Models will adjust for age, gender, and MS phenotype; EDSS and disease duration will be included as covariates if significant in preliminary models. Interactions between treatment group and MS phenotype will be tested in each model; if significant, treatment effect will be evaluated in models stratified by MS phenotype.

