The possibility of mid-study therapy regimen change for some subjects (see Exclusion criteria g. and h.) will be accounted for in analysis by running models with and without these subjects to explore the impact of these changes on analysis results. If results from the two models are consistent, all subjects will be included in the final model.

There are multiple distinct outcomes of interest in this study; since each outcome measures a unique aspect of MS progression no adjustment for multiple comparisons is planned.

Primary endpoint:

Between group differences in the odds of a 20% or greater increase in T25FW, the primary outcome measure of clinical progression of MS, will be tested at 36 months using multiple logistic regression models adjusted for covariates. Generalized

estimating equation (GEE) models will be used to test for between group differences in change over time in clinical progression (20% or greater increase in T25FW) adjusted for covariates. To test for between group differences in time to clinical progression distribution curves, Cox proportional hazards models (conditional on model assumptions being met) or Kaplan-Meier analysis will be used.

Secondary endpoints:

Safety and tolerability

To evaluate safety and tolerability of ACTH, lists and descriptive statistics of adverse events, serious adverse event, and treatment compliance will be compiled and calculated for each group at each visit. Fisher's exact tests will be used to test for between group differences in specific adverse event rates, serious adverse event rates, and treatment compliance rates.

Between group differences in mean changes in physical exam and laboratory measures (weight, blood pressure, HgbA1c, bone mineral density) will be tested using two-sample t-tests. In addition, between group differences in the proportion of subjects with abnormal blood pressure, HgbA1C, electrolyte and bone mineral density levels will be tested using Chi-square tests or Fisher's exact tests.

Change in ambulation, cognition, and global measures of MS-related disability scores

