Subjects will be asked to contact their study site if they develop new symptoms that are concerning to them. The local study coordinator will record the reported symptoms on the Unsolicited AE Form, which will be reviewed by the local investigator. An unscheduled study visit will occur if the local investigator deems these AEs as potentially serious, possibly related to study medication, and/or requiring in-person assessment. If the reported symptoms are interpreted as mild and/or unrelated to study medication, the subject may be referred to their primary physician or advised to report back by phone with updates about symptom

evolution/resolution. Unscheduled visits will not be routinely performed for suspected MS relapse (see section 7D, Relapses), although they may occur in this situation if the reported symptoms are interpreted as a possible treatment-related AE. Assessments/procedures performed at an unscheduled visit will include all of the assessments done at Visit 3 (see Table 1) with the exception of study drug distribution; any further assessments and/or procedures (e.g. physical examination, other tests, referrals) will be done at the discretion of the local investigator.

F. Early Termination and Intent to Treat

Once subjects are randomized, regardless of if or the length of time they have been on blinded treatment, they will be included in the efficacy (intent to treat) analysis if efficacy data are available (that is, if they have completed at least one annual follow-up visit). Subjects who withdraw (e.g., due to side effects) prior to completing the Month 12 visit will be asked to return the study drug to the site, and to participate in annual phone calls (Months 12 and 24), and to return to the site for the final visit at Month 36. Subjects who withdraw after completing the Month 12 visit will be asked to return the study drug to the site, and to complete the remaining annual study visits (i.e., Month 24 and Month 36) even though they are not receiving drug. Subjects are of course allowed to decline further participation, in which case they would be considered lost-to-follow-up.

G. Data Safety Monitoring

A DSMB will be formed and will consist of one MS specialist, one neurologist familiar with the evaluation and treatment of MS but not otherwise associated with the study, and the study biostatistician. A DSMB chairperson will be chosen from one of the two neurologists on the DMSB.

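### Randomising 50 per arm covers loss of the Month 36 outcome only up to 16%, not the 20% dropout anticipated; at 20% loss, 40 per arm remain and power is about 78%

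*Combined protocol and SAP*

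**What the plan says.** The sample size argument is in section 6.B (Sample Size Calculation) of the combined protocol and SAP. For worsening proportions of 0.6 and 0.3, a two-sided 0.05 test and equal arms, "42 subjects per treatment arm would provide 80% power". The next sentences read "we anticipate a dropout rate of up to 10-20% of randomized subjects" and "To account for this possibility, a total sample size of 100 subjects (50 per treatment arm) will be randomized". Section 6.B names no formula for the 42, gives no inflation formula, and does not say which rate within the range the 50 was designed for.

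Three other places decide who contributes to the primary analysis:

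- Section 6.E (Data Analysis Plan, Primary endpoint): the difference between arms "will be tested at 36 months using multiple logistic regression models adjusted for covariates". No imputation of a missing Month 36 value is described.
- Section 5.A (Ambulation): the endpoint is the proportion "who show a 20% increase in T25FW at the last study visit, compared to baseline".
- Section 7.F (Early Termination and Intent to Treat): a randomised subject enters the efficacy analysis after at least one annual visit. Those who withdraw before Month 12 are asked "to return to the site for the final visit at Month 36", and those who withdraw later are asked to attend the remaining annual visits. Finally, "Subjects are of course allowed to decline further participation, in which case they would be considered lost-to-follow-up".

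**The concern.** The increase from 42 to 50 is presented as the answer to the dropout just described, and the top of that range is 20%. A reader will take it that 80% power survives a 20% dropout. Simple division suggests otherwise, because losing one fifth of 50 leaves fewer than 42.

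At stake is whether the stated power is true at the plan's own upper dropout figure, and whether the team knows what retention the design needs. The size of the trial is not in question.

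**Working it through.** **Inputs.** All are from section 6.B: P1 = 0.6, P2 = 0.3, two-sided alpha 0.05 (z = 1.96), power 80% (z = 0.8416), 1:1 allocation, 42 per arm required, 50 per arm randomised, dropout up to 10-20%.

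**Step 1: reproduce the 42.** Pooled two-proportion formula without continuity correction, mean proportion (0.6 + 0.3)/2 = 0.45:

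n = [1.96 x sqrt(2 x 0.45 x 0.55) + 0.8416 x sqrt(0.6 x 0.4 + 0.3 x 0.7)]² / 0.3²

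= [1.96 x sqrt(0.495) + 0.8416 x sqrt(0.24 + 0.21)]² / 0.09 = 41.97, so 42.

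The plan's figure reproduces. The arcsine formula gives 41.8, also 42. The unpooled formula gives 39.2, so 40, and the continuity-corrected one gives 49. Neither matches the plan.

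**Step 2: apply the stated loss.**

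- At 20%: 50 x 0.8 = 40 per arm, below 42.
- Break-even: 1 - 42/50 = 0.16, so 16%.

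**Step 3: power at each level of loss.** Power(n) = Phi{[0.3 x sqrt(n) - 1.96 x sqrt(0.495)] / sqrt(0.45)}.

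| Loss of Month 36 outcome | Per arm | Power |
|---|---|---|
| 0% | 50 | 86.6% |
| 10% | 45 | 82.8% |
| 16% | 42 | 80.0% |
| 18% | 41 | 79.0% |
| 20% | 40 | 78.0% |

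**Step 4: what full cover would need.**

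- 10% loss: 42/0.9 = 46.7, so 47 per arm.
- 15% loss: 42/0.85 = 49.4, so 50 per arm.
- 20% loss: 42/0.8 = 52.5, so 53 per arm, 106 in total against 100 planned.

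The common but incorrect inflation 42 x 1.2 = 50.4 rounds up to 51, so 50 is not a 20% allowance on that basis either.

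**Step 5: effect of return visits.** With 20% dropout there are 10 dropouts per arm. If 0, 1 or 2 per arm return at Month 36, the numbers are 40, 41 or 42 and power is 78.0%, 79.0% or 80.0%.

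**Step 6: does the result depend on the formula?** At 40 per arm, arcsine gives 78.3% and exact enumeration of the uncorrected chi-square test gives 79.6%. The unpooled formula gives 80.7%, but it would have led to 40 per arm, not the stated 42.

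**The case against.** The strongest objection is that dropouts need not be lost to the analysis. Section 7.F admits anyone with one annual visit, and section 5.A takes the endpoint at the last study visit. Read together, a subject who leaves after Month 12 still counts. To fall below 42, at least 9 of 50 per arm (50 - 9 = 41) would need to have no annual visit at all: withdrawn before Month 12 and absent at Month 36. That is much less likely than 20% attrition over three years. This point has force, and it is why the shortfall is conditional. It does not remove the problem, because section 6.E tests at 36 months and gives no rule for a missing value, so the documents do not settle which reading applies.

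Second, section 6.B gives a range and never says outright that 80% power is kept at 20%. A round 100 covers the midpoint, 15%. That is an ordinary planning choice, but the text does not limit its claim to 15%.

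Third, the gap is about the size of the approximation error, and the pooled formula is inferred from the matching 42 because the plan names none. That is correct as to size. Still, both formulas that return 42 give less than 80% at 40 per arm, and so does exact enumeration.

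Fourth, uncertainty about the assumed proportions matters more. If P1 were 0.58 with the same halving (P2 = 0.29), pooled power at the full 42 would already be 77.4%. This is a good reason to rate the point low, but it does not make the dropout statement correct.

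**Conclusion.** The concern holds and is minor. The planned 50 per arm covers the lower and middle part of the anticipated dropout but not its upper end. The allowance runs out at 16% loss. At 20%, 40 per arm remain against 42 required, and power falls by about 2 points, from 80.0% to 78.0%.

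This rests on four assumptions: every one of the 20% lacks the Month 36 outcome, loss is equal in the two arms, the P1 and P2 of section 6.B are true, and an unadjusted two-proportion test stands in for the planned covariate-adjusted logistic regression. The shortfall shrinks or disappears if two or more dropouts per arm return at Month 36, or if an earlier visit may serve as the last study visit. The trial is phase II with safety and tolerability as its main objective, so the consequence for its conclusions is slight.

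**What to change.** Keep 100 subjects and replace the dropout sentences in section 6.B with a statement of what the sample size delivers, for example:

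*With 50 randomised per arm, 80% power is preserved for up to 16% loss of the Month 36 primary outcome; at 20% loss (40 per arm) power is about 78%. These figures assume equal loss in both arms and an unadjusted comparison of two proportions.*

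Section 6.B should also say whether its dropout figure means stopping study treatment or lacking the Month 36 measurement, since section 7.F keeps these apart. If the primary analysis is meant to use an earlier visit when Month 36 is missing, sections 5.A and 6.E should be made to agree on that, and the sentence above worded to match.

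The cost is wording only, with no change to sample size, procedures or analysis. The stated power at the upper dropout figure becomes slightly less favourable. In return, the team has a concrete retention target: the Month 36 outcome in at least 42 of 50 subjects per arm.

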Between group differences in study endpoint mean of each of the secondary outcomes: change in ambulation (6MWT, MSWS-12, Hauser Ambulation Index), change in cognition (eight subtests of the five BRB-N tests), and change in MSFC z-scores will be tested using multiple linear regression models adjusted for baseline score and other covariates. Mixed model analysis of repeated measures, utilizing data collected at all time points, will be used to test for between group differences in change over time in mean secondary outcome measures adjusted for covariates. Between group differences in the odds of EDSS progression will be tested using multiple logistic regression models adjusted for other covariates. Generalized estimating equation (GEE) models will be used to test for between group differences in change over time in progression rates adjusted for other covariates. Cox proportional hazards models (conditional on model assumptions being met) or Kaplan-Meier analysis will be used to test for between group differences in time to EDSS progression.

OCT Temporal Quadrant RNFL

OCT temporal quadrant RNFL measurements from one eye per subject will be used for analysis purposes; randomly selected unless the patient has a history of optic neuritis in which case the unaffected eye will be selected. Between group differences in change in OCT temporal quadrant RNFL thickness will be tested using a multiple linear regression model adjusted for baseline thickness and other covariates. Multiple linear regression models will also be used to test for between group differences in three year rate of change adjusted for other covariates. Separate mixed model analyses of repeated

measures will be used to test for between group differences in 1) change over time in RNFL thickness and 2) change over the 3 years in annualized rates of RNFL change.

Exploratory endpoints

Fatigue

Between group differences in study endpoint mean FSS will be tested using a multiple linear regression model adjusted for baseline FSS score and other covariates. Mixed model analysis of repeated measures, utilizing data collected at all time points, will be used to test for between group differences in change over time in mean FSS adjusted for covariates.

Other vision measures

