Multiple linear regression models will be used to test for between group differences in LCVA scores adjusted for other covariates. Binocular LCVA scores will be used to test for a treatment effect on vision changes; monocular LCVA scores will be used for correlation with OCT measures (from the matching eye). Generalized estimating equation (GEE) models will be used to test for between group differences in change over time in vision loss rates adjusted for other covariates. In addition correlation of LCVA with OCT measures (RNFL and macular volume) will be evaluated using Pearson correlation analysis (Spearman correlation will be used if measures have skewed distributions).

Between group differences in mean OCT macular volume scan measures will be tested using multiple linear regression models adjusted for covariates. mixed model analyses of repeated measures will be used to test for between group differences in change over time in OCT macular volume measures.

7. Study Procedures

A. Schedule of study procedures:

1. Symptoms questionnaire for subjective adverse events at baseline, 3, 6 and 12 months and then annually.
2. Comprehensive metabolic panel (CMP) and hemoglobin A1C (HbgA1C) at screening, 6 and 12 months, and then annually.
3. EDSS and DEXA scan (both hips/femurs and lumbar spine) at screening and then annually.
4. OCT at baseline and then annually.
5. MSFC, T25FW, 6MWT, LCVA, MSWS-12, AI, FSS and BRB-N at baseline and then annually.
6. Practice sessions (at screening visit:
 - a. BRB-N - 1 practice session

- b. PASAT - 2 practice sessions (in addition to the one administered during BRB-N)
- c. 9HP - 3 practice sessions

Table 1. Study Schedule

	V1 Screen 0 to -4 wks	V2 Baseline M0	V3 *** M3	V4 M6	V5 M12	V6 M18	V7 M24	V8 M30	V9 M36
Informed Consent	X								
Inclusion/Exclusion	X								
Injection Training		X							
Blood Pressure		X	X	X	X	X	X	X	X
Weight		X	X	X	X	X	X	X	X
Safety Lab Tests^a	X			X	X		X		X
Skin & Edema Assessment		X	X	X	X	X	X	X	X
OCT		X			X		X		X
LCVA		X			X		X		X
EDSS	X				X		X		X
Timed 25-Ft Walk		X			X		X		X
9-Hole Peg Test	XXX	X			X		X		X
PASAT (apart from BRB-N)	XX								
6 Minute Walk Test		X			X		X		X
MS Walking Scale - 12		X			X		X		X
Fatigue Severity Scale (FSS)		X			X		X		X
Hauser Ambulation Index		X			X		X		X
Brief Repeatable Battery	X	X			X		X		X
DEXA Scan^b	X ^c				X		X		X
Randomization		X							
Symptom Questionnaire		X	X	X	X	X	X	X	X
Concomitant Medications		X	X	X	X	X	X	X	X

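### The efficacy models omit the randomisation stratum (centre), and the primary model omits baseline T25FW: a modest, avoidable loss of precision that SAP wording can repair

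*Combined protocol and SAP*

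**What the plan says.** Section 6.C specifies "blocked randomization stratified by study center, with equal (1:1) allocation". The general covariate rule in section 6.E is: "Models will adjust for age, gender, and MS phenotype; EDSS and disease duration will be included as covariates if significant in preliminary models". The between-group difference in the primary endpoint "will be tested at 36 months using multiple logistic regression models adjusted for covariates", with no further list, so the general rule is all there is. Neither centre nor baseline T25FW appears in it.

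For ambulation, cognition and MSFC, section 6.E says that the outcomes "will be tested using multiple linear regression models adjusted for baseline score and other covariates". The models for RNFL thickness and fatigue also name their baseline value. Baseline T25FW is available, since section 7.A schedules "MSFC, T25FW, 6MWT, LCVA, MSWS-12, AI, FSS and BRB-N at baseline and then annually".

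Section 5.F requires a rise of at least 1.0 for EDSS progression when baseline EDSS is 2.0–5.0, and 0.5 when it is 5.5–6.0. Baseline EDSS still reaches the progression model only through the significance rule.

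Two further steps in 6.E depend on the data. On the treatment-by-phenotype interaction: "if significant, treatment effect will be evaluated in models stratified by MS phenotype". On subjects whose MS therapy changes: "If results from the two models are consistent, all subjects will be included in the final model". No threshold, preliminary model or meaning of consistency is given.

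**The concern.** A factor that restricts the randomisation should normally be in the analysis. If centres differ in progression risk and the model ignores them, the standard error does not reflect the balance that stratification achieved, and the test becomes conservative.

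Baseline T25FW is a natural candidate predictor of a 20% rise in T25FW. The plan already accepts the argument for baseline adjustment in most continuous secondary outcomes but does not carry it to the primary one. EDSS progression is similar: the size of change that counts as an event is set by baseline EDSS, so that value should not have to earn its place through a test.

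Power is at stake in a trial of 100 randomised subjects with little to spare. So is a clear statement of which model gives the primary answer.

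**Working it through.** **1. The plan's own figure.** Inputs from section 6.B: 0.60 vs 0.30, two-sided 0.05, 80% power. Mean proportion = 0.45.

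n per arm = [1.960 × √(2 × 0.45 × 0.55) + 0.842 × √(0.6 × 0.4 + 0.3 × 0.7)]² / 0.30² = 41.97, so 42. The formula has no covariate input, so the stated size stands whatever is adjusted for.

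**2. Model size.** Expected events among 84 analysed = 42 × 0.6 + 42 × 0.3 = 37.8.

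- Plan: treatment, age, gender, phenotype (2) = 5 terms, or 7 with EDSS and duration. 37.8/5 = 7.6 and 37.8/7 = 5.4 events per term.
- Adding centre (2 terms for three sites) and baseline T25FW to the fixed list: 8 terms, 37.8/8 = 4.7. With EDSS and duration as well: 10 terms, 37.8/10 = 3.8.

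**3. Power at p<0.05, by simulation.** Assumptions, none given in the documents:

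- Three equal centres with 14 per arm each, and phenotype shares of 55/35/10%.
- EDSS correlated 0.7 with log baseline T25FW.
- Overall rates of 60% vs 30%.
- Odds ratios (OR) per SD, and centre gaps in log-odds.

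The plan is read as adding EDSS and duration when p<0.05 in a joint model. The fuller model has centre and baseline but not EDSS or duration. There were 10,000 runs per row, or 6,000 in the last two; Monte Carlo error is about 0.4–0.5 points.

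| Assumed prognostic strength | Plan | With centre and baseline | Difference |
|---|---|---|---|
| None | 78.6% | 78.9% | +0.3 |
| Baseline OR 1.5, centres 0.5 apart | 80.3% | 82.3% | +2.0 |
| Baseline OR 2.0, centres 0.5 apart | 80.7% | 83.7% | +3.0 |
| Baseline OR 2.5, centres 0.5 apart | 81.0% | 85.7% | +4.7 |
| Baseline OR 2.5, centres 1.0 apart | 81.8% | 87.7% | +5.9 |
| Baseline 1.5, EDSS 1.5, centres 0.5 apart | 82.5% | 84.0% | +1.5 |
| Baseline 1.5, duration 2.0, centres 0.5 apart | 82.8% | 82.1% | −0.7 |
| Baseline 1.5, EDSS 1.5, duration 2.0, centres 0.5 apart | 85.0% | 83.4% | −1.6 |

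In the last two rows, keeping EDSS and duration in the fuller model gives 84.6% and 86.5%, which is 2.5 and 3.1 points more than leaving them out.

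**4. Where the gain comes from.** With centres 1.0 apart and no baseline effect, adding centre alone moves power from 79.6% to 84.1%, but type I error also moves from 3.8% to 5.5%. When both tests are calibrated to the same size, centre alone contributes −0.3 to +0.2 points. On that basis the first six rows become −0.6, +1.3, +2.6, +3.9, +3.0 and +0.7.

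**5. Type I error.** About 4–6% under the plan and 5.2–6.4% with centre and baseline (Wald). A likelihood-ratio test of the fuller model runs at 5.7–7.4%.

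**6. The significance rule for EDSS and duration.** Four mechanical readings (joint or univariable, 0.05 or 0.10) reach different primary decisions in 0.8–1.9% of simulated trials under the planned effect.

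**The case against.** The strongest objection is that the harm is small and the remedy is not uniformly better. Type I error is not inflated, 80% power at 42 per arm is intact, and T25FW at baseline is already the denominator of the endpoint, so the contrast with continuous outcomes is weaker than it first looks. If duration is strongly prognostic, a model that drops it in favour of centre and baseline does slightly worse than the plan. All of this stands. It limits the point to an efficiency gain and rules out presenting the removal of EDSS and duration as costless. It does not remove the case for centre, which follows from the design, or for baseline T25FW, which costs one term.

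A reader might infer that the open rules let a favourable model be chosen after seeing results, because section 6.D unblinds one investigator "as well as the study statistician and other members of the Data Safety Monitoring Board" and section 7.G has efficacy analysed every year. Taking the best of four covariate sets would give a type I error of 5.9–8.1% in simulation. The documents do not support that as a prediction. The unblinding is for safety review, nothing says that anyone selects on the treatment result, and a rule applied mechanically stays near 5%. The gap is that the plan does not say when the choice is fixed.

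A reader might also infer that subjects who change therapy will be dropped. Section 6.E presents that comparison as exploratory and never says they are removed, and section 7.F includes randomised subjects with follow-up regardless of time on treatment.

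**Conclusion.** The point holds as a cheap improvement. Centre is missing from every efficacy model despite stratified randomisation, baseline T25FW is missing from the primary model, and baseline EDSS is only conditional in the EDSS-progression model. The trial is not invalidated and the sample size does not change.

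The size is about 0 to 5 points of power at p<0.05 in most scenarios. It reaches 5.9 when baseline and centre are both strongly prognostic, and is slightly negative (−0.7 to −1.6) when duration is strongly prognostic and left out. The gain comes from baseline T25FW and, if centres differ strongly, from centre as well; part of the centre share only restores a conservative test to its nominal level. These figures rest on assumed prognostic strengths, centre sizes and correlations. The textual omissions do not.

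**What to change.** In section 6.E:

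- **Primary model.** Add study centre and log baseline T25FW to age, gender and MS phenotype, and name the Wald test for treatment. Set a pooling rule for small sites in advance, because section 7.C allows sites to be added. With h subjects per arm, the chance that a site has all or no events is 0.28^h + 0.18^h: 46% for 2 analysed subjects, 11% for 4 and 0.7% for 8.
- **EDSS and disease duration.** Replace the significance rule with a decision, made before any unblinded efficacy analysis, to have both in or both out. Report the other version as a sensitivity analysis.
- **Other efficacy models.** Add centre throughout, and baseline EDSS to the EDSS-progression model.
- **Primary conclusion.** State that it comes from this one model in all intent-to-treat subjects, with the therapy-change and phenotype-stratified analyses supportive.
- **Time point.** Reconcile section 5.A (last study visit), section 6.E (36 months) and section 7.F (at least one annual visit). Until then the analysis set has no single meaning.

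The cost is SAP wording only, since the added variables are already collected. The statistical price is three more terms for about 38 expected events (about 4–5 per term, depending on the EDSS and duration decision) and a Wald test size of about 5.5–6.5%. The odds ratio becomes conditional on more covariates, so a standardised risk difference should be reported beside it.
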